Blinding: At the central site (OHRI), the research assistant will give a unique identifier number to each image, for a random quality control and for cross referencing whenever needed. The cropped images, as detailed below, will not have the subject ID visible to the PI at the time of reading but will be accessible for the quality control. (read-only access). The research assistant at OHRI is the only site personnel who has the capacity to uncrop the images in the PowerPoint file (password protected files).

For interim analysis, image reading will be performed after the first 10 patients. Final reading will be done after all patients are recruited. Images will be scored by the principal investigator at OHRI. Images will not contain any identifiable information such as Date of Birth (DOB) or initials. The US images will be transferred to a PowerPoint file by the research assistant at OHRI in JPEG

format. The research assistant will generate an unblinded master list, inaccessible to other site personnel, to link the slide numbers with the patients and scanned anatomical sites and the slide will have no other information on the patient number or ID. For scoring the images by the PI, a random order slide show will be conducted, irrespective of the machine used or the anatomical site or patient assessed, to ensure blindness to data related to the patient identifiers (The PI will not be blinded to the machine that the image was taken with as the JPEG format that is achieved from different machines are identifiable, but due to the random order scoring, images that belong to the same joint by the different machines are not to be scored consecutively). There will be nine separate powerpoint files, for images of joints, tendons, entheses, nail including power Doppler and gray scale findings; and grey scale file for erosions. Scoring will be done using previously validated methods as detailed below.

During the data collection, there will be interim analysis: Interim analysis will be done after 10 patients being recruited. The readings and scorings will be done by the principal investigator at OHRI center, following the exact methodology as above.

The grading of greyscale intraarticular synovitis and power Doppler intrasynovial signals will be done based on the OMERACT definitions (scales of 0-3) as follows^{16, 17} :

Greyscale inflammatory (hypoechoic) synovial hyperplasia:

- **Grade 0:** no hypoechoic synovial hyperplasia

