The study will be registered on clinicaltrials.gov including a study report at the end of the study. The results will be presented in EULAR 2023 congress and subsequent national and international rheumatology congresses. A manuscript will be generated to be published in a peer reviewed rheumatology journal with the possibility of subsequent publications on post-hoc analysis. To be eligible to be included in publications, investigators will be required to have a significant contribution to one of the following aspects of the study, in compliance with the ICMJE (International Committee of Medical Journal Editors) recommendations and criteria:

- 1) Conception of the study and development of the methodology. This will include members of the steering and advisory committee.
- 2) Data collection. Each investigator will be required to recruit 10 cases.
- 3) Data analysis
- 4) Contribute to the publication by reviewing and approving the final abstract/manuscript.

Timetable:

Action	Timeframe
Ethics application- approval	September-October 2022
Contracts	November-December 2022
Recruitment	January -April 2023
Analysis and Abstract submission for ACR 2023 congress and subsequent national and international rheumatology congresses	May 2023
Writing the manuscript	May-July 2023

References

2. Filer A, de Pablo P, Allen G, Nightingale P, Jordan A, Jobanputra P, Bowman S, Buckley CD, Raza K. Utility of ultrasound joint counts in the prediction of rheumatoid arthritis in patients with very early synovitis. *Ann Rheum Dis*. 2011 Mar;70(3):500-7. doi: 10.1136/ard.2010.131573. Epub 2010 Nov 29. PMID: 21115552; PMCID: PMC3033529.

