2.2. Randomization and Blinding

Study patients will not be randomized to any group. The same anatomical regions will be evaluated with the same ultrasound protocol for each patient included in the study. The scoring of the US images will be done blindly by the principal investigator at OHRI as stated below.

At the central site (OHRI), the research assistant will give a unique identifier number to each image, for a random quality control and for cross referencing whenever needed. The cropped images, as detailed below, will not have the subject ID visible to the PI at the time of reading but will be accessible for the quality control. (read-only access). The research assistant at OHRI is the only site personnel who has the capacity to uncrop the images in the PowerPoint file (password protected files).

Images will not contain any identifiable information such as Date of Birth (DOB) or initials. The US images will be transferred to a PowerPoint file by the research assistant at OHRI in JPEG format. The research assistant will generate an unblinded master list, inaccessible to other site personnel, to link the slide numbers with the patients and scanned anatomical sites and the slide will have no other information on the patient number or ID. For scoring the images by the PI, a random order slide show will be conducted, irrespective of the machine used or the anatomical site or patient assessed, to ensure blindness to data related to the

patient identifiers (The PI will not be blinded to the machine that the image was taken with as the JPEG format that is achieved from different machines are identifiable, but due to the random order scoring, images that belong to the same joint by the different machines are not to be scored consecutively). There will be nine separate powerpoint files, for images of joints, tendons, entheses, nail including power Doppler and gray scale findings; and grey scale file for erosions.

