2.4. Statistical Interim analyses and stopping guidance

An interim analysis will be done after 10 patients. In the interim analysis, the agreement between the images obtained with the handheld ultrasound and the images on the gold standard device will be compared after the blinded scoring. A moderate level of agreement (defined as a kappa value of >0.40) between the two tools in the interim analysis will allow parallel initiation of subsequent studies proposed in the research framework. The results of this interim analysis will not be used to adjust the design of the remainder of the study. We do not have any formal stopping rules for the trial.

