2.5. Timing of final analysis

After all sites recruit 10 patients each, the data will be verified and locked. Final analysis will commence once the final lock has been confirmed by the Principal Investigator.

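### The sole reader, who can recognise the machine, scores both the interim and the final images, and nothing in the plan withholds the interim kappa from that reader

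*Protocol*

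**What the plan says.** Protocol 4.3 names one reader: "Images will be scored by the principal investigator at OHRI". It sets two reading occasions: "For interim analysis, image reading will be performed after the first 10 patients. Final reading will be done after all patients are recruited". For the interim it repeats: "The readings and scorings will be done by the principal investigator at OHRI center, following the exact methodology as above".

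SAP 2.2, like Protocol 4.3, is open about the limit of the masking: "The PI will not be blinded to the machine that the image was taken with". The safeguards described are:

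- subject identifiers are cropped from view;
- the slide order is random;
- "images that belong to the same joint by the different machines are not to be scored consecutively";
- the list linking slides to patients and sites is held by the research assistant alone.

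Protocol 4.0 states the aim of keeping readers blind to clinical findings and to the other modality's scores.

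SAP 2.4 gives the interim criterion, "A moderate level of agreement (defined as a kappa value of >0.40"), which releases later studies. Protocol 4.4 ties it to the primary outcome. SAP 2.4 adds that the interim will not alter the design and that there is no formal stopping rule. Protocol 8.0 dispenses with a Data Monitoring Committee. For the end of the study, SAP 2.5 says: "Final analysis will commence once the final lock has been confirmed by the Principal Investigator".

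Neither document says who calculates the interim kappa, who receives it, or whether the reader is kept from it.

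**The concern.** The primary endpoint is a visual yes/no call on synovitis in B mode, made by one person who can recognise the device. Such a call depends on the reader's threshold for a borderline image. If that person learns the agreement achieved in the first third of patients, and knows that it governs the start of further work, the threshold for handheld images can move in the remaining reading, consciously or not. The final kappa would then partly reflect the feedback and not only the device. The primary result is judged against 0.61 (Protocol 4.5, SAP 2.3), so a modest shift in scoring matters.

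**Working it through.** **1. Inputs.** Kappa 0.61, prevalence 20%, confidence interval width 0.15, 683 joints, 30 patients with 24 joints each (Protocol 4.5, SAP 2.3); 95% confidence (SAP 3.1); interim after 10 patients (SAP 2.4). Joints are treated as independent, as the plan's own figure does.

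**2. The plan's sample size reproduces.** With k = 0.61, p = 0.20, w = 0.15, z = 1.96 and equal marginals:

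n = 4z²(1−k)[(1−k)(1−2k) + k(2−k)/(2p(1−p))]/w²

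- (1−k)(1−2k) = 0.39 × (−0.22) = −0.0858
- k(2−k)/(2p(1−p)) = 0.8479/0.32 = 2.6497
- 0.39 × (2.6497 − 0.0858) = 0.9999
- n = 4 × 3.8415 × 0.9999/0.0225 = 682.9, so 683 joints.

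The set-up behind the illustration is therefore the sponsor's own.

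**3. Timing and precision.** The interim falls at 10/30, one third of the patients: 240 of 720 joints. At kappa 0.61 the 95% interval width, 2 × 1.96 × √(0.9999/n), is 0.253 at 240 joints (0.483 to 0.737) and 0.146 at 720 joints (0.537 to 0.683).

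**4. The 2x2 table at kappa 0.61, prevalence 20% on both machines.**

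- each discordant cell: p(1−p)(1−k) = 0.16 × 0.39 = 0.0624
- both positive: 0.20 − 0.0624 = 0.1376
- both negative: 0.80 − 0.0624 = 0.7376
- observed agreement: 0.1376 + 0.7376 = 0.8752

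**5. A stricter threshold for handheld images.** Suppose a fraction f of handheld positives is called negative, whatever the gold-standard call. Observed agreement becomes 0.8752 − 0.1376f + 0.0624f. The handheld positive rate becomes 0.20(1−f).

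| f | Observed agreement | Chance agreement | Kappa |
|---|---|---|---|
| 10% | 0.8677 | 0.18×0.20 + 0.82×0.80 = 0.692 | 0.1757/0.308 = 0.570 |
| 20% | 0.8602 | 0.16×0.20 + 0.84×0.80 = 0.704 | 0.1562/0.296 = 0.528 |

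**6. If only the last 480 joints are affected.** The documents do not say whether the first 10 patients are re-read or their interim scores carried forward. If carried forward, one third of the joints keep the table in step 4:

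- f = 10%: agreement (0.8752 + 2×0.8677)/3 = 0.8702; handheld rate (0.20 + 2×0.18)/3 = 0.1867; chance 0.688; kappa 0.1822/0.312 = 0.584.
- f = 20%: agreement (0.8752 + 2×0.8602)/3 = 0.8652; handheld rate (0.20 + 2×0.16)/3 = 0.1733; chance 0.696; kappa 0.1692/0.304 = 0.556.

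**7. Does a blanket shift raise kappa?** Not from a symmetric table. Take kappa 0.50 at 20% prevalence (cells 0.12, 0.08, 0.08, 0.72):

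- under-calling 10% of handheld positives: agreement 0.836, chance 0.692, kappa 0.144/0.308 = 0.47;
- over-calling 5% of handheld negatives: agreement 0.808, chance 0.24×0.20 + 0.76×0.80 = 0.656, kappa 0.152/0.344 = 0.44.

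The fractions f and the starting tables are assumptions. They show how sensitive kappa is; they do not estimate what would happen.

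**The case against.** The plan has real safeguards. Without identifiers or the master list, with slides in random order and the two images of a joint kept apart, the reader is not given the pairing of handheld and gold-standard scores. SAP 2.4 bars design changes, and nothing states that the reader will see the interim kappa. All of this stands and narrows the concern. However, a shift in threshold for one device needs only recognition of the device, which the plan concedes, and a bar on design changes does not govern scoring.

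A reader might infer more than the documents support:

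- **That the principal investigator could push kappa past 0.61 by resolving discordant joints.** That requires knowing which joints disagree, which the linking rules withhold. Step 7 shows that a blanket shift from a symmetric table lowers kappa. Selective re-calling of borderline images, or a shift that corrects an existing imbalance between machines, could raise it, but the documents do not allow either to be quantified.
- **That the interim tells the reader in which direction handheld calls differ.** The described output is a kappa, which has no direction. No passage sends the reader a 2x2 table or image comparison, though none rules it out.
- **That the reader personally recruited or scanned a third of the patients.** The basis is "Each investigator will be required to recruit 10 cases", which stands among the authorship criteria in Protocol 8.0. Protocol 4.2 gives the clinical assessment to an experienced rheumatologist at each site, and no passage says who recruits or scans at OHRI. An analysis without the OHRI patients would in any case mix site, operator and patient differences and would not test interim feedback.
- **That the principal investigator's confirming the lock is a fault.** SAP 2.5 already puts the final analysis after the lock.

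**Conclusion.** The concern holds as an unclosed route to bias, not as evidence of bias. One reader who is not masked to machine scores a subjective primary endpoint twice, and the plan leaves that reader free to learn the interim agreement in between. The size of any effect is unknown.

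The illustration runs from kappa 0.61 to 0.57 or 0.53 if 10% or 20% of handheld positives were under-called in all 720 joints, and to 0.58 or 0.56 if only the last 480 were affected. It assumes 20% prevalence on both machines, a symmetric starting table and independent joints. The largest of these shifts, about 0.08, is similar to the half-width of the planned final interval (0.146/2 = 0.073), and recruiting more joints would not reduce it.

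This is a cheap improvement worth making. It does not invalidate the design, and it leaves untouched the reader's ability to recognise the machine, which the plan discloses.

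**What to change.** Add to SAP 2.4, with a matching sentence in Protocol 4.3 or 4.4:

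- The research assistant at OHRI, who already holds the master list, or a statistician other than the reader, computes the interim kappa.
- Only the result above 0.40, or not above 0.40, is released. That is all the decision on follow-on studies needs.
- The value, the 2x2 table and any image-level comparison are withheld from the reader until all final image scores are locked.

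The cost is a few sentences. No extra reader, patients or images are needed and the sample size does not change. The downside is that the principal investigator sees the interim value only after the lock. Some feedback remains, because a result of not above 0.40 itself signals low agreement, but it is far less than the kappa and the table would give.

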4.5 Sample Size Consideration

Study agreement analyses will be done per joint. To give a kappa ≥ 0.61 (from substantial interrater agreement to almost perfect agreement) with a confidence interval width of 0.15 and the expectation of approximately 20 % of joints assessed having any synovitis in B mode (based on a previous study by our group), 683 joints would be required.¹⁸ This corresponds to 30 patients if 24 joints per patient are assessed. Non-inferiority margin will be $\kappa \geq 0.61$.

5.0 Impact of the study

The relatively low cost of the hand-held US devices makes them affordable for the everyday rheumatology practices, including the community and academic centers. Although the study is focused on PsA patients, the wide range of lesions that will be investigated in this study will help to prove the validity of the hand-held US in comparison to the high-end machines for other uses of US in the field of rheumatology. We hope that our results will increase the uptake up MSK US in daily practice that will allow earlier diagnosis and more accurate assessment of disease activity on a large scale. US itself has been characterized as more sensitive than either X-ray or Magnetic Resonance Imaging (MRI) at detecting joint involvement in PsA.²¹ Adding to this increased sensitivity, handheld POC US also has the potential to accelerate the patient journey to diagnosis

and optimized therapy by circumventing the long waiting lists associated to MRI imaging that plague the Canadian healthcare system. In fact, the Conference Board of Canada estimates that, by 2022, the average wait will be 133 days for MRI, greatly exceeding the acceptable target of 30 days²². This is concerning when it has been shown that, for PsA, a diagnostic delay of more than 6 months (180 days) is associated to irreversible joint damage and poor functional outcomes.

6.0 Translation of CRF

The physician Case Report Form (CRF) does not need to be translated. The patient CRFs and consent forms will be available in English and in French. The PROs have already been validated in French.

7.0 Ethical and regulatory aspects

The primary site for ethics submission will be the Ottawa Hospital/the Ottawa Hospital Research Institute; [name]. The Principal Investigator is [name].

7.1 Participant consent

Eligible patients will be approached for study recruitment during their visits in rheumatology. Patients who are willing to participate will be asked for a signed informed consent. All patients will receive detailed information about the study at the time of enrollment. The participants will have the opportunity to leave the study at any time. According to the participant's will data previously recorded could be kept in the database for analysis, in case they withdraw consent.

7.2 Personal information management

The local investigators will keep a confidential correspondence list of patient identifiers and of patient numbers. The centralized information will consist entirely of de-identified data.

7.3 Regulations and Review Board

The study will be conducted in accordance with the protocol, Good Clinical Practice (GCP), ethical principles that have their origin in the Declaration of Helsinki and all applicable local regulations.

Independent Ethics Committee or Institutional Review Board approval of the protocol will be obtained prior to commencing the study at each site, through the principal investigator and designated investigators.

An Institutional Review Board approved, study-specific informed consent will be reviewed, signed and dated by the subject (and the investigator) prior to the performance of any study-related procedures.

8.0 Data Quality Assurance

Data management

Patients will be identified by a local number at each investigator site, which will have a 2-letter code for a site and a number for each patient. Each site will keep a confidential subject identification code list, so that if there are missing data this information will be available locally to clarify the information.

Two paper CRFs, patient and physician CRFs, will be filled for each patient during the visit and these will be the source documents. The CRFs will be scanned and uploaded to the SharePoint at each center, within 3 day after the visit. In addition, US images of each patient will be uploaded to the SharePoint. US images and CRFs uploaded from each center will be reviewed by the research assistant at Ottawa Hospital Research Institute (OHRI) center. If there are any missing or erroneous data, it will be ensured that the errors and deficiencies are corrected by contacting the center. Any queries will be confirmed with the site within a week of the data entry. Center will then correct and update the physician CRF as per Good Documentation Practices and re-scan the CRF to the sharepoint. Then the analyzed CRFs data will be transferred to Research Electronic Data Capture (REDCap) (version 12.4.18 - © 2023 Vanderbilt University) by the research assistant at OHRI.

After all the data is transferred to REDCap, the data in Sharepoint will be deleted. The data in REDCap will also be deleted when the data is exported and the analysis is completed. The exported data will be locked and stored in a secure and password protected computer at The Ottawa Hospital, according to the requirements by the Research Ethics Board (REB) at The Ottawa Hospital. The paper CRFs, which are the source documents, will also be maintained on site for 10

years . The electronic data will be stored for 15 years. For both devices already being Health Canada and FDA approved, a Data Monitoring Committee is not deemed to be needed by the PIs.

Publication, Study Results and Authorship Criteria

The study will be registered on clinicaltrials.gov including a study report at the end of the study. The results will be presented in EULAR 2023 congress and subsequent national and international rheumatology congresses. A manuscript will be generated to be published in a peer reviewed rheumatology journal with the possibility of subsequent publications on post-hoc analysis. To be eligible to be included in publications, investigators will be required to have a significant contribution to one of the following aspects of the study, in compliance with the ICMJE (International Committee of Medical Journal Editors) recommendations and criteria:

- 1) Conception of the study and development of the methodology. This will include members of the steering and advisory committee.
- 2) Data collection. Each investigator will be required to recruit 10 cases.
- 3) Data analysis
- 4) Contribute to the publication by reviewing and approving the final abstract/manuscript.

Timetable:

Action	Timeframe
Ethics application- approval	September-October 2022
Contracts	November-December 2022
Recruitment	January -April 2023
Analysis and Abstract submission for ACR 2023 congress and subsequent national and international rheumatology congresses	May 2023
Writing the manuscript	May-July 2023

References

2. Filer A, de Pablo P, Allen G, Nightingale P, Jordan A, Jobanputra P, Bowman S, Buckley CD, Raza K. Utility of ultrasound joint counts in the prediction of rheumatoid arthritis in patients with very early synovitis. *Ann Rheum Dis*. 2011 Mar;70(3):500-7. doi: 10.1136/ard.2010.131573. Epub 2010 Nov 29. PMID: 21115552; PMCID: PMC3033529.

1.1. Background and Rationale

Recently, ultrasonography (US) has experienced a rapid evolution in the field of rheumatology, an evolution certainly driven by the broad applicability of point-of-care (POC) US for the assessment of rheumatic diseases. Despite the use of US in many other medical fields, such as gynecology, emergency or gastroenterology for much longer, the uptake by the rheumatology community was only initiated in the last two decades. This is mostly due to the fact that most of the structures that are assessed in rheumatology are very superficial, and the technology to generate a high resolution view for these superficial structures, to a degree of being able to detect even mild inflammatory changes, have been developed relatively recently.

Nowadays, rheumatologists typically use US for guided injections and for the assessment of joint structures, connective and vascular tissues, and related pathologies.¹ When it comes to the assessment of musculoskeletal (MSK) structures, the value of US lies upon a unifying principle for many arthritides: rapid detection of highly relevant and often times subclinical features of disease. For example, in a rapidly progressing disease like Rheumatoid Arthritis (RA), US allows faster detection of synovitis and bone erosion, resulting in earlier fulfillment of diagnostic criteria.²

Early disease detection with US perhaps takes its most relevant sense in psoriatic arthritis (PsA), where efforts are currently being deployed to intercept disease in its transition from psoriasis (PsO).

Moving on to the subject of ultrasonography scanners as medical devices; more specifically the high quality US scanners and high-resolution transducers required for the practice of rheumatology. A number of barriers persist and stand in the way of a wider use of POC US for the detection, diagnosis and management of rheumatic diseases. A significant one is the acquisition and maintenance costs of high quality instruments. There are recent technical and technological advances in the field of handheld ultrasonography that are set to overcome the access barrier. Typically, the cost of acquisition of scanners with a greyscale frequency of at least 13 MHz and a Doppler frequency of at least 8 MHz ranges from 25000CAD to

90000CAD. Hand-held US technology promises to take this cost down to a price tag under 10,000CAD with the introduction of affordable high-definition scanners possessing the specifications/requirements for use in the rheumatology practice (Greyscale frequency: 12 - 20 MHz and Doppler frequency: 8 - 12 MHz). Clarius Mobile Health Inc., an innovative company based out of Vancouver B.C., produces such devices. Clarius US scanner have regulatory approval by the FDA and Health Canada. However, before they can be specifically used for the practice of rheumatology, their performance needs to be validated against gold-standard devices for key interventions.

US holds significant promise as an imaging tool in rheumatology and in the future, handheld US could be used at the bedside to provide diagnostic and prognostic information, as well as guide both systemic and local treatment decisions and applications. Through the accurate assessment of disease extension and activity (e.g. presence of enthesitis in a PsA patient presenting with primarily as synovial disease), the bedside application of US in standard assessment of the PsA patients will enable the understanding of which domains are involved and would require treatment/and which treatment based on the domain involved. There are numerous advantages of the hand-held US devices over the existing gold standard devices for being accessible by more physicians, therefore by more patients. The ability to carry the device in their pocket will allow the physicians to be able to use in multiple settings, e.g. in different offices or inpatient vs outpatient clinics. Making the bedside US a part of the clinical assessment will avoid any delays in diagnosis and lead to earlier treatments. In addition, it increases the patients adherence to therapy adjustments.³ As such, the goal of this trial will be to validate two affordable handheld MSK US scanner against gold-standard devices through an assessment of their accuracy for:

- visualizing anatomical structures and pathologies
- detecting vascular flow

